15.3. Objective

To identify stratification biomarkers for sorafenib-based treatment for hepatocellular carcinoma.

This comprises the following three specific goals:

- (1) Identify serum proteins that correlate with response to treatment with sorafenib.
- (2) Identify cancer cell genome copy number variations that correlate with response to treatment with sorafenib.
- (3) Identify cancer cell gene mutations that correlate with response to treatment with sorafenib.

15.4. Subjects

Patients who are enrolled in the main study and have consented to participate in the translational study.

15.5. Exclusion Criteria

Not specifically defined.

15.6. Enrollment Procedures

Enrollment process for the translational study

- (1) Each participating institution will obtain consent for both the main study and the translational study.
- (2) Each participating institution will enroll patients for the translational study at the same time as the main study and will fax forms to the data center. The specific method for enrolling patients in the translational study is to check the box for “enroll in the translational study” on the Enrollment Eligibility Form.
- (3) The data center will confirm eligibility and then enroll the patient in both the main study and the translational study.
- (4) The data center will record the translational study sample number for the patient on the Enrollment Confirmation and Assignment Notification Form and send it by reply fax. The same number will be used for the patient enrollment number and translational study sample number.
- (5) Each participating institution will collect samples, write the translational study sample number on the label, and store the samples at their institution.

Contact information and hours for inquiries about the translational study:

SILIUS-TR Data Center: **[name]** (Department of Genome Biology, Kindai University Faculty of Medicine)

[contact]

[contact]

E-mail: [contact]

Hours: Monday through Friday, 9:00 AM to 5:00 PM (except December 29 to January 3)

Contact information for inquiries about samples:

Translational study manager: **[name]** (Department of Genome Biology, Kindai University Faculty of Medicine)

[contact]
 [contact]
 E-mail: [contact]

15.7. Handling of Samples

15.7.1. Types and quantities of samples

- (1) Peripheral blood, 4 mL x 3 time points
- (2) Tumor tissue biopsy specimen, one specimen

15.7.2. Timing of sample collection

- (1) Peripheral blood (serum)
 Samples will be collected at three time points: before treatment (Pre), 1 month after treatment (Day 29), and when treatment is discontinued due to progressive disease (PD) (no response).
 - (1) Pre: The “Pre” sample should be collected during the period after the time of consent but before the start of treatment.
 - (2) Day 29: The “Day 29” sample may be collected ± 7 days from day 29 after starting treatment.
 - (3) PD: The “PD” sample may be collected up to 14 days after PD is diagnosed. This sample should also be collected if treatment is discontinued for any other reason.
- (2) Tumor tissue biopsy specimen
 Should be collected during the period after the time of consent but before the start of treatment.

15.7.3. Sample processing

See “Sample Processing Procedures”. The data center will send designated blood collection tubes, microcentrifuge tubes, saline, sample labels, and dispensing pipettes in advance to institutions able to enroll patients for the translational study. They will use the Laboratory Request Form if necessary.

Peripheral blood

Four milliliters of peripheral blood will be collected. Each 4-mL sample will be collected using the designated 4-mL blood collection tubes sent by the data center (VP-AS054K50, sealed with red film). Serum will be isolated, the translational study sample number will be recorded, and the sample will be dispensed and stored frozen.

Once frozen, the sample may not be thawed.

Procedures for serum isolation	
1	Collect 4 mL of blood in the designated blood collection tube. Slowly invert 6 times.

2	Let rest at room temperature for 30 min.
3	Centrifuge (1500 g for 10 min at room temperature)
4	Dispense the serum into three microcentrifuge tubes using the dispensing pipette (about 0.5 mL x 3 tubes).
5	Record the translational study sample number in two places on the microcentrifuge tubes (top and side) with a permanent marker.
	Translational study enrollment number (SL3-○○○)-Pre/ -Day29/ -PD)
6	Freeze and store in a freezer at –20°C to –80°C.

Serum will be obtained under the above conditions as far as possible. Samples can be stored at –20°C at participating institutions for up to 6 months. After that point, they will be sent to the sample receiving destination. Samples can be stored at –80°C at participating institutions for an indefinite period of time. The sample number on serum samples will consist of the translational study enrollment number plus a code for the collection time point, as follows: SL3-○○○-Pre or SL3-○○○-Day29 or SL-○○○-PD.

Tumor tissue biopsy specimen

One tumor tissue biopsy specimen will be collected by liver biopsy (ultrasound-guided needle biopsy). A total of 0.5 mL of sent saline will be added to a microcentrifuge tube and the collected biopsy specimen will be added to the saline. The translational study sample number will be recorded on the microcentrifuge tube and the sample stored frozen at –20°C to –80°C. The sample number recorded on the tumor tissue biopsy specimen will be “Translational Study Sample Number-Bps (SL3-○○○-Bps)”.

Sample	Collection container	Processing methods/translational study sample number	Storage container	Storage conditions
Blood (serum)	4 mL Vacuum blood collection tube	3 tubes for centrifugation/dispensing SL3-○○○-Pre/Day29/PD	1.5 mL microcentrifuge tube	-20 to -80°C
Tumor tissue biopsy specimen		1 specimen SL3-○○○-Bps	1.5 mL microcentrifuge tube with 0.5 mL of saline	-20 to -80°C

15.7.4. Shipping of samples

Every 6 months after the start of the study, each participating institution will receive a fax

from the SILIUS-TR data center requesting that frozen stored samples be sent. At that time, the corresponding site investigator will be sent Styrofoam for packing samples. They will include a List of Sent Specimens and Samples with the samples and send still-frozen samples to the Department of Genome Biology at Kindai University Faculty of Medicine. However, depending on the sample storage capacity of the institution, samples may also be sent for one patient at a time. The translational study sample number should always be recorded in two places (top and side) on the sample. The following shipping methods apply to both serum and tumor tissue biopsy specimens. It is preferred that they be sent at the same time.

- (1) Check that the following day is a weekday.
- (2) Prepare the designated Styrofoam box (sent by the data center).
- (3) Fill with dry ice and seal the designated Styrofoam box with packing tape.
- (4) Be sure to send the box by frozen delivery service. (Frozen serum samples may not be thawed.)

Costs associated with shipping (including dry ice and frozen delivery fees) will be paid by the study coordinator (when shipping, be sure to get a receipt and submit a Sample Shipping Fee Reimbursement Form for reimbursement.)

Where to send samples:

Sample Storage Manager

Department of Genome Biology, Kindai University Faculty of Medicine

[name]

[contact]

[name]

TEL /[contact]

15.7.5. Storage and disposal of samples

Samples will be stored at the laboratory of the Department of Genome Biology, Kindai University Faculty of Medicine. The sample storage manager is [name] of the Department of Genome Biology, Kindai University Faculty of Medicine. Serum and tumor tissue biopsy specimens will be stored in a deep freezer at -80°C . The storage location will be secured by two or three levels of locks, including the entrance to the research building and the constantly locked laboratory door and deep freezer door.

Samples will be stored for up to 3 years after the final analysis for the study. Once the storage period has elapsed, samples will be disposed of if there is no particular reason not to do so. Samples will be disposed of in the event that the patient who provided the sample requests to withdraw their consent, the sample number is unrecognizable due to problems

with the label or computer, the sample was or was suspected to have been collected improperly or contaminated, or a researcher deems disposal necessary for any other reason. Such samples will have the sample number removed before disposal. If the provider of the sample requests to withdraw their consent and the sample is being stored at a participating institution, the responsible party at that institution will be contacted and the sample will be disposed of promptly. If the sample is being stored at Kindai University, it will be disposed of after the study coordinator is contacted.

15.7.6. Management of personal information and anonymization

The personal information manager will anonymize samples in a linkable fashion on patient enrollment. Specifically, they will record the linking code (translational study sample number) on the Enrollment Confirmation and Assignment Notification Form and notify the institution by fax.

Assistant personal information managers are staff members at each institution responsible for linking personal information with the linking code (translational study sample number). Upon notification of linking codes, the assistant personal information manager will record the codes on samples from their institution (no other information besides the linking code and Pre/Day29/PD may be recorded on samples). Therefore, although samples identified by linking code will later be sent from each participating institution to the measuring facility, no identifying personal information will be sent to staff involved in measurements and analysis. The chart for linking personal information to linking codes will be controlled by the data center and each participating institution, disposed of as appropriate, and kept under strict control to ensure no information containing personal information is leaked.

*The same number used for the patient enrollment number will be used as the linking code (translational study sample number).

15.8. Study Methods

15.8.1. Measurement of blood angiogenic factors and growth factors

Angiogenic factors (cytokines and chemokines) and growth factors in patient serum will be quantified by multiplex ELISA or ELISA (ELISA will be used if the measurement range is not appropriate for multiplex ELISA). Measurements will be performed in serum collected before treatment, on day 29, and after PD using a Bioplex suspension array system manufactured by Bio-Rad. Measurements will be performed in the laboratory of the Department of Genome Biology, Kindai University Faculty of Medicine. Data from these measurements will be used to assess correlation with response to treatment with sorafenib (e.g., response, PFS, and OS) and identify factors predicting response. The following are examples of markers that might be measured:

Amphiregulin, Beta-cellulin, EGF, EGFR, Epregrulin, FGF-basic, HB-EGF, PDGF-BB, PIGF, Tenascin C, TGF-alpha, HGF, IL-1 α IL-1 β , IL-2 α , IL-2R, IL-3, IL-4, IL-5, IL-6, IL-7, IL-8, IL-9, IL-10, IL-12, IL-13, IL-15, IL-16, IL-17, IL-18, basic FGF, CTACK, Eotaxin, G-CSF, GM-CSF, GRO- α , HGF, ICAM1, IFN- α 2, IFN- γ , IP-10, KC, LIF, MCP-1, MCP-3, M-CSF, MIF, MIG, MIP-1 α , MIP-1 β , MIP-2, β -NGF, PDGF-BB, RANTES, SCF, SCGF- β , SDF-1 α , TNF- α , TNF- β , TRAIL, VCAM-1, and VEGF. (See Translational Study Table 1)

15.8.2. Measurement of cancer cell genome copy number variations

DNA will be extracted from collected tumor tissue biopsy specimens and cancer cell genome copy number variations will be detected by comparative genomic hybridization (CGH). CGH detects variations in copy number in the whole genome (including excessive genomic DNA, deletions, and amplifications) in a short period of time. Because CGH can detect changes in copy number for genes in the cancer genome, it is now widely used to analyze genomic abnormalities in solid tumors, which were previously difficult to analyze in detail with chromosomal analysis. It can determine what losses and amplifications in copy number have affected the physical size of the genome at the chromosomal level. This method cannot detect reciprocal chromosomal translocations not accompanied by changes in copy number. Copy number variations in sorafenib target genes and genes related to angiogenesis will be analyzed to assess correlation with response to treatment with sorafenib and identify factors predicting response. Measurements will be performed at Kindai University Faculty of Medicine. Results will be verified by PCR.

15.8.3. Measurement of cancer cell gene mutations

Mutations in VEGFR2-like receptor families (e.g., VEGFRs, FGFRs, PDGFRs, and KIT) and BRAF, which are target molecules for sorafenib, will be analyzed. Mutations in major oncogenes and tumor suppressor genes will also be investigated. The OncoCarta panel is an analytical technology based on time of flight mass spectrometry that can measure 239 mutations in 19 genes at once (See Translational Study Table 2). Gene mutations will also be detected by direct sequencing and correlations with response to treatment with sorafenib will be assessed.

15.9. Biostatistical Analysis

Correlations between clinical data provided by the data center and various measured parameters will be analyzed at the Department of Genome Biology at Kindai University Faculty of Medicine and the Department of Medical Informatics at Niigata University Medical and Dental Hospital. Data on the degree of expression of quantified serum proteins,

gene copy numbers at about 250,000 loci in the cancer cell genome, and mutations in sorafenib target genes and major oncogenes will be obtained in this study. The following statistical methods will be used to analyze correlations between these measured data and clinical parameters. CGH analysis will be performed using Partek Genomic Suite 6.4 software (Partek Inc., St Louis, MO). Analysis of correlations of measured data with progression-free survival and overall survival will be performed using the Cox proportional hazards model. The clinical utility of factors as biomarkers will be evaluated by multivariate analysis with adjustment for clinical factors. In addition, differences in survival between subgroups will be compared with the log-rank test. Correlations between biomarkers and response rate will be assessed with Fisher's exact test. Statistical analysis will be performed and graphs created with SAS for Windows (ver. 9.1.3) or Medcalc for Windows (ver. 11.1.1).

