5.3. Randomization and Stratification Factors

Patients will be randomized into the low-dose FP plus sorafenib group (combination therapy) or the sorafenib group (monotherapy) in a 1:1 ratio. Group assignments will be made using a computer program.

The following items will be used as stratification factors for randomization with the minimization method.

- (1) Institution
- (2) Macroscopic vascular invasion (MVI) (Vp0, Vp1-3, Vp4)
- (3) Presence/absence of extrahepatic spread (EHS)

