6. TREATMENT PLANS AND CRITERIA FOR ADJUSTING TREATMENT

6.1. Protocol Treatments

6.1.1. Low-dose FP and sorafenib group (combination therapy group) (Table 1)

This study will use the following doses demonstrated as safe in a phase I/II study of sorafenib and low-dose cisplatin/fluorouracil hepatic arterial infusion chemotherapy for advanced hepatocellular carcinoma. Cisplatin will be administered at a dose of 20 mg/m² on day 1 (within 30 days), and fluorouracil will be administered at a dose of 330 mg/m²/day by hepatic infusion using a reservoir for 5 days from day 1 through day 5 (continuous infusion over 24 h), followed by 2 days off. This sequence will be repeated for 2 weeks, followed by 2 weeks off. Sorafenib will be administered continuously at a dose of 400 mg twice daily for 28 days from day 1 to day 28. This 4-week period constitutes one cycle.

The first cycle of treatment will be started within 28 days of randomization. Treatment with sorafenib before hepatic arterial infusion chemotherapy will be allowed. However, patients must be off sorafenib for 2 days before and 7 days after reservoir placement. The next cycle of treatment will be started within 14 days. Sorafenib will be continued until the start of the next cycle. This combination therapy will be continued until discontinuation of the protocol treatment.

If an adverse event is observed, treatment will be interrupted or the dose will be reduced as appropriate in accordance with **6.3.2. Criteria for adjusting the sorafenib dose (dose interruption and reduction)** and **Section 6.3.3. Criteria for Hepatic Arterial Infusion Chemotherapy (Low-dose FP) Dose Adjustment (Dose Interruption and Reduction)**. After the protocol treatment is discontinued, appropriate treatment as described in **Section 6.5 Post-trial Treatment** will be instituted.

The arterial catheter should be placed in a manner that allows for proper drug distribution throughout the liver, and the flow should always be checked by contrast CT through the port or by DSA before starting treatment.

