predictors of response to sorafenib have investigated factors such as blood VEGF and VEGFRs, tumor vessel density, and tumor VEGF expression, but no useful biomarkers have been identified. Therefore, evaluation of the clinical utility of various blood cytokines, chemokines, and growth factors could lead to the identification of new biomarkers that predict response to treatment and resistance to treatment. The antibody suspension bead arrays system (Bio-Rad Laboratories) can assess 30 to 50 cytokines and chemokines at once under the same conditions and its clinical utility for biomarker discovery has been established.^{2,3} Blood cytokines, chemokines, and growth factors other than VEGF can reduce sensitivity to a drug through the phenomenon of escape, and thus would be significant to include in a study investigating potential predictors of response to sorafenib. This research group has previously shown that the pre-treatment serum concentration of various growth factors is a useful noninvasive biomarker of response to molecularly targeted drugs.⁴ Predictors of response to sorafenib will be identified using methods established in that clinical study.

(2) Cancer cell genome copy number variations

Amplifications and losses in copy number that affect the physical size of the cancer cell genome at a chromosomal level can be the essential etiology of many solid cancers and leukemia. However, copy number variations in certain loci seen in examples such as leukemia and brain cancers are known to define the malignancy and prognosis of the tumor. Genome copy number variations of sorafenib target genes in cancer cells may be useful predictors of response to treatment with sorafenib as tumor factors predicting response.

(3) Cancer cell gene mutations

It is widely recognized that activation of target molecules of molecularly targeted drugs through gene mutations can be a predictor of response. Therefore, mutations in VEGFR2-like receptor families (e.g., VEGFRs, FGFRs, PDGFRs, and KIT) and BRAF, which are target molecules for sorafenib, will be analyzed.

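### The biomarker sub-study seeks predictors of response to sorafenib, but both arms receive sorafenib and the stated analysis names neither treatment arm nor a marker-by-arm interaction

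*Protocol*

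**What the plan says.** **Aim.** Section 15.3 states the objective as "To identify stratification biomarkers for sorafenib-based treatment for hepatocellular carcinoma". Its three goals share one pattern, for example "Identify serum proteins that correlate with response to treatment with sorafenib", and repeat it for copy-number changes and mutations. Section 15.2 is more explicit: "Predictors of response to sorafenib will be identified using methods established in that clinical study". Section 15.8.1 counts tumour response, PFS and OS alike as measures of response to sorafenib.

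**Design.** Section 5.3 randomises patients to "the low-dose FP plus sorafenib group (combination therapy) or the sorafenib group (monotherapy) in a 1:1 ratio". Section 6.1.1 says of the combination arm: "Sorafenib will be administered continuously at a dose of 400 mg twice daily". Section 6.1.2 gives sorafenib to the monotherapy arm in the same terms.

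**Analysis.** Section 15.9 relates the marker data to PFS and OS with Cox models, uses multivariable models adjusted for clinical covariates, and relates markers to response rate with Fisher's exact test. It adds that "differences in survival between subgroups will be compared with the log-rank test". It mentions neither treatment arm nor an interaction.

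**Copy-number scope.** Section 15.9 lists "gene copy numbers at about 250,000 loci in the cancer cell genome" among the data to be obtained. Section 15.8.2 says "Copy number variations in sorafenib target genes and genes related to angiogenesis will be analyzed".

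**The concern.** A marker used to choose who should get sorafenib has to show that the drug's effect differs by marker level. That needs patients with and without the drug, and this trial has none without it. A marker may look like a predictor of sorafenib benefit when it only identifies patients who would live longer on any treatment.

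The second difficulty is that half the patients also receive low-dose FP. If the arms are pooled and arm is not in the model, a marker of response to the infusion can be reported as a marker of response to sorafenib.

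At stake is how the results are labelled and used. Sections 15.2 and 15.12 describe the intended use as treatment stratification, including sparing patients a drug that will not help them. The randomised comparison, which could inform selection for the combination, is left unused in the stated analysis.

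**Working it through.** The protocol gives no significance level, power or sample-size calculation for the sub-study. The only related figure to reproduce is the phase I response rate in Section 2.4.3: 7 PR among 7 + 7 + 2 + 2 = 18 patients, and 7/18 = 38.9%, as stated.

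**1. What the design can identify.** Let M be a marker, S an indicator for sorafenib and F an indicator for low-dose FP. Write the log hazard as

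b·M + s·S + g·(M×S) + f·F + d·(M×F).

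Here b is prognosis, g is prediction of sorafenib benefit, and d is prediction of benefit from added FP. Everyone has S = 1, so the marker coefficient in the monotherapy arm is b + g. In the combination arm it is b + g + d. The data identify b + g and d, but never g alone. With 1:1 allocation and no term for arm, the pooled coefficient is roughly b + g + d/2, which mixes all three. No later choice of test changes this.

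**2. Tumour response.** Section 2.8 says sorafenib alone has a low response rate but gives no number. Call it r, and take the phase I 38.9% for the combination. With equal arms, the share of responders who come from the combination arm is 0.389 / (0.389 + r). This exceeds one half whenever r is below 38.9%, and it is two thirds if r is half that figure. A pooled Fisher's test would then rest mainly on responses to which FP may have contributed.

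**3. Baseline and later samples.** Randomisation balances pre-treatment markers between arms on average, so for these the omission of arm causes mixing and not confounding. Section 15.8.1 also uses serum from day 29 and from PD. Treatment can change those levels, so for them arm can affect both marker and outcome.

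**4. What the interaction could detect.** Section 15.11 targets 80% to 90% of enrolled patients: 0.8 × 190 = 152 and 0.9 × 190 = 171. Assume the same share of the 112 planned deaths: 89.6 to 100.8, or about 90 to 101. Assume also a marker split 50/50 and a two-sided 5% level.
- Main effect, 80% power: HR = exp[(1.960 + 0.842) × 2/√deaths] = 1.81 with 90 deaths and 1.75 with 101.
- Marker-by-arm interaction: the standard error doubles, so the detectable ratio of hazard ratios is the square of the main-effect HR: 1.805² = 3.26 and 1.746² = 3.05.

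Only very large interactions would be detected with good power.

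**5. Number of loci.** Under a global null, expected false positives = number of tests × level. The level is an assumption throughout.
- All 250,000 loci tested singly: 12,500 at 5%, 2,500 at 1%, 250 at 0.1%.
- Candidate loci only, assumed 50 to 2,500 because Section 15.8.2 gives no count: 2.5 to 125 at 5%.

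The two sections therefore leave a range from a few to 12,500 at an unadjusted 5%.

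**The case against.** The best defence has four parts.

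- **The goals speak of correlation with response, and the objective of sorafenib-based treatment, which describes both arms.** Read literally, the planned tests address that. This stands for the narrow wording of the goals. It does not cover the promise of predictors in Sections 15.2 and 15.8 or the stratification use in Section 15.12. Tumour response is also not a purely prognostic endpoint, but it still has no sorafenib-free comparison, and FP contributes to it in one arm.
- **The work is exploratory, and Section 15.13.2 requires validation.** True, and this limits the weight of the point. But what must be validated there is reproducibility. Reproducing an association in patients who all take sorafenib would not separate prediction from prognosis. The section does not describe the validation design, so one with a sorafenib-free group is not excluded.
- **Model terms and error control may sit in an analysis plan not shown.** This stands for multiplicity, whose absence here is not a finding. It does not rescue the aim, which the design cannot meet whatever terms are added.
- **A marker-by-arm interaction answers a different question from the stated one.** Also true: it concerns added FP. It is nevertheless the only predictive question for which the trial has randomised evidence.

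A reader might infer from the 250,000 loci that each is tested separately and that thousands of false positives will follow. The protocol does not support this. Section 15.9 says the data will be obtained, not that every locus gets its own test; Section 15.8.2 points to candidate genes; and no significance level is given.

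**Conclusion.** The point holds as a mismatch between aim, design and stated analysis. With sorafenib in both arms, associations with OS or PFS cannot be attributed to sorafenib benefit as opposed to prognosis, and pooled responses may reflect low-dose FP. This rests on the protocol's own text and needs no numerical assumption. The detectable interaction of about 3.0 to 3.3 depends on the assumed 90 to 101 deaths and an even marker split; it shows that the added analysis would be hypothesis-generating.

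On multiplicity, what holds is only that Sections 15.8.2 and 15.9 do not make clear which loci are tested. The figure of 12,500 applies solely if all loci were tested singly at an unadjusted 5% with none associated, and should not be taken as a property of the plan.

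The matter is minor for the trial as a whole. It leaves the primary OS comparison and safety untouched, and bears on what the sub-study may claim.

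**What to change.** - **Section 15.9:** include treatment arm in every Cox model, stratify the log-rank and response-rate comparisons by arm, and add an exploratory marker-by-arm interaction with a statement that its power is low.
- **Sections 15.3 and 15.8, and the matching sentence in 15.2:** describe marker main effects as associations with outcome under sorafenib-based treatment, not as predictors of sorafenib benefit. Present the interaction as concerning benefit from added low-dose FP.
- **Sections 15.8.2 and 15.9:** state which loci enter the association analysis, candidate genes or the whole array, and refer to wherever the error-control rule is kept.

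The changes should be settled before marker data are linked to outcomes. They need no extra patients, samples or visits. The cost is a more modest claim for the sub-study and an interaction analysis that will often be inconclusive.

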15.11. Target Sample Size and Period

The enrollment target for the translational study is 80% to 90% of the patients enrolled in the main study. The enrollment period will be the same as that for the main study.

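### Section 15.9 relates biomarkers to response rate by Fisher's exact test alone, so quantified serum proteins must be cut at an unstated point, with avoidable loss of power for that endpoint

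*Protocol*

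**What the plan says.** Section 15.9 of the Protocol lists three kinds of measurement: "Data on the degree of expression of quantified serum proteins", followed by "gene copy numbers at about 250,000 loci in the cancer cell genome, and mutations in sorafenib target genes and major oncogenes will be obtained". It then assigns methods to outcomes.

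- For survival outcomes: "Analysis of correlations of measured data with progression-free survival and overall survival will be performed using the Cox proportional hazards model". The log-rank test is added for comparisons between subgroups.
- For response: "Correlations between biomarkers and response rate will be assessed with Fisher's exact test".
- In general: "The clinical utility of factors as biomarkers will be evaluated by multivariate analysis with adjustment for clinical factors". No model, endpoint or covariate is named for this analysis.

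Section 15.8.1 says the serum factors are quantified by multiplex ELISA or ELISA. It gives response, PFS and OS as examples of the outcomes they will be related to. Section 15.8.2 describes the copy-number work as detecting excess DNA, deletions and amplifications, checked by PCR. Sections 15.8 and 15.9 contain no cut-point for any marker. On size, section 15.11 says: "The enrollment target for the translational study is 80% to 90% of the patients enrolled in the main study".

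**The concern.** Fisher's exact test works on counts in a table. It suits a mutation that is present or absent. It cannot take a concentration, so for serum proteins the analyst must first choose a threshold. Two things follow. Information within each category is discarded, so a protein that truly differs between responders and non-responders is missed more often than the samples require. The result also depends on where the threshold is placed, and that choice is open for each of several dozen proteins.

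The same section keeps the measured value for PFS and OS through the Cox model, so the loss arises for response alone. Finding serum proteins that correlate with response to treatment is the first of the three goals in section 15.3, and response is one of the outcomes by which section 15.8.1 would judge it.

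**Working it through.** Section 15 states no power, significance level, effect size or cut for biomarkers, so there is no figure of the plan's own to reproduce. The check asks how much power the cut costs under plausible inputs.

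**Inputs from the Protocol**
- Main study: 190 patients (section 12.1).
- Sub-study: 0.80 × 190 = 152 to 0.90 × 190 = 171 (section 15.11).
- Response rate: 38.9% in the phase I study of the combination (section 2.4.3). Section 2.8 calls the sorafenib response rate low without giving a figure.

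**Assumptions**
- Pooled response of 15%, 25% or 38.9%.
- Marker normal on the log scale, with responders shifted by d standard deviations.
- Cut at the sample median; two-sided 0.05.
- d from 0.4 to 0.8, since the documents give no effect size.

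**Method.** For each patient, response ~ Bernoulli(p) and marker ~ N(d × response, 1). Fisher's exact test on the median split is compared with the Wilcoxon rank-sum test on the uncut value. With 3,000 to 4,000 simulated trials per setting, each power has a standard error of at most √(0.25/3,000), about 0.9 points.

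| n | Response | d (SD) | Fisher, median cut | Wilcoxon | Loss (points) |
|---|---|---|---|---|---|
| 152 | 15% | 0.6 | 44% | 71% | 27 |
| 152 | 25% | 0.5 | 48% | 73% | 25 |
| 152 | 38.9% | 0.5 | 61% | 83% | 22 |
| 171 | 25% | 0.5 | 57% | 78% | 21 |
| 171 | 38.9% | 0.6 | 84% | 96% | 12 |

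Over all combinations with d from 0.4 to 0.6 the loss is about 10 to 27 points; the ends move by a point or two between runs. At d = 0.8 it is about 2 to 22 points, because both tests approach full power when response is common.

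**Further checks**
- Stricter level, as would suit many markers (0.001; n = 152, 25% response, d = 0.8): Fisher 42%, Wilcoxon 76%.
- No true difference, nominal 5%: Fisher rejects about 3% to 5% of the time and Wilcoxon about 5%.
- Source of the loss: at n = 152, 30% response and d = 0.50, the t-test on the uncut value has 80% power, a chi-square test on the split 63%, and Fisher's test on the split 48%. About 17 of the 32 points come from the cut and 15 from the exact test's conservatism. In other settings, such as n = 171 with 30% response, the chi-square and Fisher results coincide and the whole loss comes from the cut.
- Wider inputs (response from 10%, d from 0.3 to 0.8, median or upper-quartile cut, against the t-test): the loss runs from about 2 to 36 points.

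**The case against.** The strongest objections concern scope.

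- **Not every biomarker is affected.** A reader might infer that the plan forces all markers into categories. It does not. Mutations are categorical already. Section 15.8.2 speaks of deletions and amplifications, which may be called as gain, loss or neutral, and section 15.9 assigns the CGH analysis to dedicated software. Nothing says copy number will be tested against response as a continuous value. This objection stands: the firm case is serum proteins, with copy number included only if it is analysed as a value.
- **The goals of section 15.3 do not rest on response rate alone.** They concern response to treatment, which section 15.8.1 illustrates with PFS and OS as well. A protein missed by Fisher's test still has two Cox analyses. This stands, and it limits the consequence.
- **The multivariate analysis may keep proteins continuous for response.** It may, but no model or endpoint is given, so it cannot be counted on.
- **Cut-points belong in the statistical analysis plan.** They may be set there. The point is not that a cut is missing, however. The Protocol names a test that needs a cut for a measurement that does not.
- **The aim is stratification, which needs groups.** A threshold can be sought once an association is found; detecting the association does not require one.
- **Section 15.13.2 calls the work exploratory and in need of validation.** This stands and sets the severity. A marker missed at this stage would, however, be less likely to reach validation.

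**Conclusion.** The point holds in a limited form. For serum proteins against response rate, and for copy number only if used as a value, the named test requires a cut that the Protocol does not give and loses power that the same samples could provide.

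Under the stated assumptions the loss is about 10 to 27 points at 0.4 to 0.6 SD and about 2 to 22 points at 0.8 SD. A reader might take this as a fixed cost per marker. The documents do not support that: effect size, response rate, cut and significance level are all assumed, and for mutations there is no loss. The existence of the loss is firm; its size is illustrative.

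Severity is minor. The overall survival analysis of the main trial and the Cox analyses of biomarkers are unaffected.

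**What to change.** In section 15.9, replace the sentence on response rate with wording to this effect:

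- Fisher's exact test is used for categorical markers (mutation present or absent; copy-number gain or loss calls).
- Serum protein concentrations, and copy number when analysed as a value, are compared between responders and non-responders on the continuous scale with the Wilcoxon rank-sum test.
- Logistic regression on the log-transformed value, adjusted for treatment group, supplies the model-based estimate. Further covariates are added only as the number of responders allows.

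The last limit matters. At 15% response and n = 152 there would be about 0.15 × 152 ≈ 23 responders, too few for a model with many covariates. The simulation supports the unadjusted Wilcoxon comparison; a multi-covariate logistic model was not simulated and should not be credited with the same gain.

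The cost is a small wording change, with no new samples, assays or patients. The drawback is that results for proteins are no longer a simple 2×2 table; grouped displays can still be shown descriptively.
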